Low back pain (LBP) is one of the most common causes of disability in the US workforce and one of the costliest to manage, with prevalence increasing up to 170% in the last 15 years. Opioid use for LBP is widespread and long-term, substantially contributing to the current dependence crisis, which has led to an NIH initiative for the development of new LBP therapies. The sacroiliac joint (SIJ) is thought to be the source of LBP in up to 30% of patients. Clinical trials have demonstrated at least moderate treatment effect of steroid and anesthetic injection (SAI) for pain. However, due to poor long-term effectiveness and associated deleterious systemic effects of steroids, other therapies for SIJ pain have emerged. Platelet-rich plasma (PRP) is a therapy in which autologous serum containing growth factors is obtained from whole blood for injection. The proposed mechanism is enhancement of tissue healing. PRP has been used for various spinal pain indications, and a recent meta-analysis concluded up to level III evidence for intradiscal treatment, but level IV for other spine structures (epidural space, facet joints, and sacroiliac joints) due to paucity of trials. For the SIJ, only one clinical trial has been performed which demonstrated significantly greater long-term pain reduction compared to SAI; however, patients were not blinded to procedure type, and inclusion diagnosis was made by physical examination without diagnostic block. Although PRP shows promise, the quality of evidence remains low, warranting more rigorous investigation. We propose to perform a randomized controlled single-blind trial of PRP versus SAI for the treatment of SIJ pain and hypothesize that PRP will demonstrate superior pain and functional outcomes compared to SAI at 3 months, and potentially result in quantifiable joint-related changes by advanced imaging.

Primary Aim: To compare the mean change in pain control, as measured by numeric rating scale, from baseline to 3 months among patients with chronic sacroiliac joint dysfunction with therapeutic platelet-rich plasma (PRP) vs. steroid/anesthetic injection (SAI).

Secondary Aim: To compare mean change in disability in patients with chronic SIJ dysfunction with PRP vs. SAI therapy by Modified Oswestry Disability Questionnaire, Short Form-12 survey, functional testing, and opiate usage assessment at 3 months.

Tertiary/Exploratory Aim: To compare mean intraarticular and periarticular MRI parameters (T1 relaxation time/T2 intensity and periarticular diffusion and perfusion) signal changes in chronic SIJ dysfunction with PRP vs. SAI therapy at 6 months.

Hypothesis: PRP will demonstrate superior pain control and disability outcomes compared to SAI at 3 months, and potentially result in intraarticular chondroprotection and/or anti-inflammatory periarticular changes that will be quantifiable using advanced MRI techniques.

Background and Significance

Prevalence and costliness of low back pain

Low back pain (LBP) is one of the most common causes of US workforce disability, and due to its effect on productivity and resultant lost wages, one of the costliest conditions to manage.¹⁻⁴ It is estimated to affect up to two thirds of people in their lifetime and is only increasing in prevalence (up to 170%).^{1,5} Likewise, therapies for chronic LBP including opioid use, spinal injections, and surgery have also increased in the last two decades, with opioids the most commonly prescribed medication, used long-term in nearly 76% of cases.⁶⁻⁹ Because of increasing incidence and recurrence, LBP makes up a substantial amount of the rising healthcare costs over the past two decades, exceeding over \$100 billion per year.^{1,10} Additionally, long-term opiate usage in LBP has substantially contributed to the opioid crisis.⁹ This has led to a translational research initiative from the National Institute of Health (NIH Back Pain Consortium [BACPAC] Research Program) to develop more effective therapies for this prevalent and debilitating condition.¹¹

Sacroiliac joint pain

The sacroiliac joint is (SIJ) thought to be the pain generator in up to 30% of cases of LBP.⁵ Chronic pain can be separated into mechanical sacroiliitis (joint instability with or without periarticular inflammation) and non-mechanical etiologies (spondyloarthropathies). Instability is related to the angle of the weight-bearing joint, possibly contributing to the slight increased prevalence in females who have a more horizontal joint surface¹², as well as with dysfunction of the regional stabilizing ligaments (iliosacral, iliolumbar, sacrotuberous, sacrospinal ligaments).¹³ Pain localization is performed by a combination of history, imaging, physical examination, and diagnostic block.¹³ Multi-test physical maneuvers have shown to be promising for localization

in many cases (sensitivity of 78-94%, specificity of 79-85%).¹⁴ However, they have not received reliable consensus¹⁵ and the diagnostic standard remains pain reduction with intra-articular anesthetic injection.¹⁶

PRP Mechanism of Action

PRP is thought to enhance tissue healing at the site of injection, related to release of growth factors and cytokines within platelets and serum.¹⁷ The PRP mechanism of action is through chondroprotection by platelet-derived growth factor which promotes proteoglycan synthesis and supports chondrocytes,¹⁸ and transforming growth factor which induces chondrogenesis.¹⁸ Additionally, PRP contains multiple anti-inflammatory markers, such as hepatocyte growth factor.^{19,20} Platelet released growth factors also stimulate formation of hyaluronic acid, the deficiency of which plays a substantial role in osteoarthritis.^{21,22} An *in-vivo* on injured rabbit knees demonstrated marked cartilage regeneration using both leukocyte poor and leukocyte rich PRP.¹⁸ Studies support that PRP is effective not only in cartilage protection and regeneration but also anti-inflammation— both of which play a role in musculoskeletal pain.

PRP Clinical Trials

PRP has been used throughout the musculoskeletal system with positive results,²³⁻²⁶ with promise particularly seen in the spine.²⁷⁻³⁴ A recent meta-analysis of spine PRP trials assigned level III evidence to intradiscal PRP; however, other areas of the spine were assigned level IV evidence due to a paucity of quality clinical trials (epidural space, facet joints, and sacroiliac joints).³¹ Specifically in the SIJ, there has been only one clinical trial which demonstrated longer efficacy for pain relief from PRP compared to SAI.³² Though results were promising, patients were not blinded to the procedure type, and diagnosis of SIJ pain was made only by physical examination without diagnostic SIJ block. Image guidance was also performed with ultrasound which cannot verify intraarticular needle placement.³⁵ In the investigators clinical trial of PRP SIJ therapy, the investigators will improve on the methodology by optimally screening patients with a diagnostic SIJ block, conducting the trial with patient blinding, and confirming intraarticular needle placement by using CT guidance. The investigators study design will improve the quality of evidence related to the use of PRP for SIJ pain, which is currently limited.³¹ This is an area of great importance, as the current treatment of SIJ pain relies heavily on steroids which have known deleterious systemic effects with repeated use including osteoporosis with increased fracture risk, and metabolic changes including blood sugar elevation in diabetics,³⁵⁻³⁸, and opioids which can lead to dependence.^{9,36-39} PRP SIJ injection with no known significant side effects has great promise to be more cost effective over time when compared to SAI.

Imaging evaluation of PRP related changes

The investigators have performed T2-mapping and T1-rho imaging sequences that sensitively evaluate cartilage^{44,45} in the SIJ of a healthy volunteer. The investigators technique demonstrated superb delineation of the SI joint space in T1-rho for region of interest analysis and for T2-intensity mapping, with T1-rho demonstrating low relaxation times

(expected in normal cartilage) (Figure 1). Intravoxel incoherent motion (IVIM) is a sequence that measures both diffusion and perfusion within soft tissue by using multiple b-values –the lower of which are sensitive to vascular motion and the higher which are sensitive to cellular motion.⁴⁶ This sequence is able to measure, and

differentiate, both diffusion and perfusion parameters without the usage of intravenous contrast. IVIM has previously been found to differentiate acute inflammation from chronic inflammation along the SIJ in subjects with ankylosing spondylitis.⁴⁷ The investigators have used IVIM in prior studies evaluating both diffusion and perfusion changes in swine models after treatment of the facet medial branch with radiofrequency ablation (RFA), allowing quantification of perfusion and diffusion changes in the treatment area.⁴⁸ As this sequence has been found to be feasible in evaluating SIJ inflammation (a component of SIJ dysfunction), the investigators will use it to quantitatively measure periarticular inflammation changes after SAI and PRP therapy.

[figure not shown]

Figure 1: T1 rho sequence through the sacrum with color map demonstrating a range of relaxation times (in msec). The SIJ demonstrates low relaxation times (arrows) in this healthy volunteer.

Experimental Design

Design: After obtaining IRB approval, the investigators will perform a prospective randomized controlled single-blind trial to assess superiority of platelet-rich plasma to steroid/anesthetic in the treatment of chronic SIJ pain.

Inclusion criteria:

- Adult (>18 y/o) males and females referred for therapeutic injection to the investigators spine interventional service with a clinical diagnosis of SIJ pain confirmed by history and at least 3 of 6 provocative physical examination maneuvers localizing pain to the SIJ.
- 50% or greater reduction in pain by a diagnostic anesthetic block⁴⁹ using no more than 1.5 cc 2% lidocaine performed under imaging guidance by a pain interventionalist (PM&R, Pain Anesthesia, or Neuroradiology Spine Intervention).
- Baseline pain must be >/=4 by numeric rating scale (NRS)⁵⁰, at least 6 weeks in chronicity, and must not be multi-factorial (related to radiculopathy or axial pain localizing elsewhere) by physical examination or confounding medical history (infection, inflammatory spondyloarthropathy, or osseous metastatic disease).

Exclusion criteria:

- SIJ steroid treatment within the prior 6 months.
- Patients with a history of infection currently on antibiotic therapy
- Usage of systemic immunosuppressants
- Pregnancy

Sample Size: Since the SIJ PRP trial paper by Singla et al did not report an estimate of the standard deviation of the visual analog scale results (which are equivalent to NRS but performed visually instead of verbally)⁵⁰, a reasonable range of standard deviations between 2 and 3 were considered in the investigators sample size calculation. A study with 20 subjects per study arm will have 80% power to detect a difference of NRS ranging from 1.8 to 2.7 using a 2-sample t-test with a 2-sided 5% type 1 error:

Standard Deviation	NRS Delta
2	1.8
2.5	2.3
3	2.7

The investigators hypothesize detection of this range of deltas is achievable. To mitigate for potential drop-out or loss to follow-up (estimated at 20%), the investigators will enroll 25 subjects per arm. Between the University of Utah and Salt Lake City VA Medical Center, the investigators spine interventional group performed a total of 54 sacroiliac joint SAI on 52 individuals in the past 12 months and 5 PRP injections on 4 individuals in the past 6 months referred in combination from the Anesthesia Pain Service and PM&R at the VA (43 individuals) and Neurosurgery at the University of Utah (9 individuals). Additionally, [name] from the PM&R service performs approximately 80 SIJ injections per year at the University of Utah and will be an additional referral partner in the investigators study equaling approximately 136 individuals/year available for recruitment in one

year (272 individuals/2 years). From this referral base the investigators are confident in meeting the minimum goal of enrolling 25 subjects/year for a total of 50 subjects in the two-year study period.

Acquired Clinical Data: age, sex, BMI, history of smoking and diabetes, and current pain medication requirements (specifically initial dosing requirements and time to refill) will be obtained through chart review.

Procedural protocol: Patient randomization will be stratified by site and performed through the RedCap database system which will be available within the procedure room. Equal allocation to 1 of 2 exposure groups will be performed: PRP and SAI. At procedure start 20 mL of blood will be drawn from the patient (no matter which group they are randomized to in order to maintain consistency between procedure types). Following this, a clinical nurse will administer the PROs and functional assessments and then exit the room. The research coordinator will perform the randomization through RedCap, and the assigned injectate (PRP or SAI) will be drawn by the physician and injected into the patient (who is blinded to the injectate type).

- PRP therapy: The SIJ will be localized under CT fluoroscopy. Local lidocaine anesthetic will be provided at the entry site. A 22-gauge Quincke needle will be advanced into the SIJ under CT fluoroscopic guidance. After autologous whole blood centrifugation with the Cascade Autologous Platelet System each sample will be evaluated with a platelet counter to assess integrity of the PRP injectate and specify leukocyte rich vs. poor preparation. Autologous platelet-rich plasma (generally 3-5 cc yield after centrifugation) will be injected into the SIJ after activation with calcium chloride.
- SAI therapy: The SIJ will be localized under CT fluoroscopy. Local lidocaine anesthetic will be injected at the entry site. A 22-gauge Quincke needle will be advanced into the SIJ under CT fluoroscopic guidance. 40 mg depomedrol mixed with 2 mL of 0.25% bupivacaine will then be injected in the SIJ (total of 3 mL).

Approximately 30 minutes following, the clinical nurse blinded to group allocation will re-enter the room and again perform patient assessments. The patient will then be given general post-injection instructions, be asked their preferred method of contact, and be discharged. The patient will remain blinded to the procedure arm throughout the study. A blinded research assistant will remotely contact the patient to obtain NRS and opiate measures at 3 and 7 days, and 2 months post-procedure. A blinded clinical nurse will perform in-person functional and disability assessments and obtain NRS and opiate measures at 1 and 3 months post-procedure.

Primary Aim

Outcomes and their measurements: The primary outcome of pain will be assessed using NRS which will be recorded pre and immediately post treatment in person, at 3 days, 1 week and at 1, 2, and 3 months post-procedure.

Analyses: The investigators will compare the two groups with respect to a mean difference in NRS from baseline to 3 months using a two-sample t-test as the investigators primary endpoint analysis. The investigators will provide 95% confidence intervals to indicate the uncertainty in these estimates. Additional analyses will evaluate the mean difference at 3 days, 1 week, 1 and 2-months post-treatment. A subanalysis will also be performed in subjects who had 80% relief by diagnostic block to determine the effect of the diagnostic cutoff.

Secondary Aim

Outcomes and their measures: The secondary outcomes of disability and quality of life will be analyzed using the Modified Oswestry Disability Questionnaire (MODQ)⁵², Short Form 12 (SF-12) Health Survey⁵³ scores, and opiate usage (by Morphine Equivalent Dose) as reported by the patient and chart review.

Functional outcomes will be analyzed by the following two tests which have been previously validated to assess physical status⁵⁴:

- The “get-up and go test”⁵⁵: The time (in seconds) that it takes a patient to rise from a chair, walk three meters, turn around, walk back to the chair, and sit down is measured.
- The “5 time sit to stand test”⁵⁶: The time (in seconds) it takes the patient to rise from sitting to standing 5 times is measured.

Disability and functional assessments will be performed in-person pre-procedure, immediately post-procedure, as well as 1 and 3 months post procedure. Additionally, reported opiate usage will be assessed at the same time periods as NRS as in the primary aim.

Analyses: The investigators will compare the two groups with respect to a mean difference in survey (SF-12, MODQ) scores from baseline to 3 months using a two-sample t-test as the investigators secondary endpoint analyses. This will also be done to assess the results of the physical functional tests, as well as reported opiate usage. The investigators will provide 95% confidence intervals to indicate the uncertainty in these estimates. A

responder analysis⁵⁷ will also be performed with at least a 2-point reduction in NRS at 3 months compared to baseline used as the endpoint, with a separate analysis performed on those who improved by 50%. Responder analyses will also be performed on MODQ and SF-12 results that meet the minimally important clinical change.^{58,59} Comparison of proportions will be performed with Fishers' exact test.

Tertiary/Exploratory Aim

Design: This will be an exploratory study to investigate MR imaging biomarkers in SIJ pain and determine whether there are changes in cartilage or periarticular signal with PRP and SAI therapy between baseline and 6 months. Additionally, differences in cartilage or periarticular signal between symptomatic and asymptomatic joint pain within the same individual will be investigated in both baseline and 6 months studies.

Inclusion criteria: Unilateral SIJ pain and all additional criteria from primary aim. This will allow comparison to baseline scan as well as comparison to an asymptomatic joint within the same patient.

Exclusion criteria: MRI contraindications per ACR guidelines and all additional criteria from primary aim.⁶⁰

Sample Size: 5 subjects will be recruited from each exposure group (PRP and SAI) for imaging analysis (10 patients total).

Acquired Clinical Data: See primary and secondary aims.

Advanced MR Imaging Parameters: MRI will be obtained pre-procedure as a baseline (at least one week after diagnostic block to ensure resolution of procedural changes), then again 6 months after SAI or PRP to measure T1 and T2 maps, as well as perfusion/diffusion properties.^{24,40}

The following sequences will be obtained with the following parameters:

T2 mapping: TR = 500 ms, ETL = 9, TE = 15, 30, 45, 60, 75 msec; bandwidth = 500 Hz/pixel; spatial resolution 1x1x3 mm³; acquisition matrix = 256x84x32

T1 rho: 3D FLASH: slice thickness 3 mm, FOV = 256 mm, resolution = 1x1x3 mm³; averages = 2, imaging; matrix = 256x256x16, 25% slice oversampling; 12 shots per each spin-lock duration; TR/TE = 6/3 ms, group TR = 4000 ms; bandwidth/pixel = 560 Hz/pixel; spin-lock durations : 0, 10, 20, 30, 40, 50 ms; B1 field: 500 Hz (1.18 Gauss); acquisition time = 8:00 min

IVIM: DWI in 3 planes (resolution = 1.8 x 1.8 x 3.3 mm) using the following b-values: 0, 10, 20, 30, 50, 80, 100, 200, 400, and 800 s/mm².⁴⁷ A STIR sequence will also be performed to evaluate periarticular inflammation.⁶¹

Post-Processing: Using a home developed processing software, which was developed using Python 3.x programming language, T2 and T1Rho maps are constructed by pixel-by-pixel fitting of the measured T2-weighted images and T1Rho source images to a function "single-exponential + constant" with respect to the echo-times (TE) and spin-lock durations, respectively. Osirix will be used for IVIM post-processing and region of interest (ROI) analysis.

Outcomes and their measurements: T1rho: cartilage relaxation time calculated in msec. T2 mapping: cartilage T2 intensity measured in regions of interest. IVIM: Perfusion parameters calculated by f (perfusion fraction), D* (pseudodiffusion), and fD*. Diffusion parameters calculated by D (tissue diffusion).

Analyses: The investigators will compare the two groups with respect to a mean difference in T1rho relaxation time from baseline to 3 months using a two-sample t-test as the investigators tertiary endpoint analyses. This method of analysis will also be performed for T2 mapping intensity, as well as IVIM parameters as stated above. The investigators will provide 95% confidence intervals to indicate the uncertainty in these estimates. The investigators will compare the mean parameters of the symptomatic joint to the contralateral asymptomatic joint within the same subject using a paired t-test and provide 95% confidence intervals to indicate the uncertainty in these estimates.

References

2. From the Centers for Disease Control and Prevention. Prevalence of disabilities and associated health conditions among adults--United States, 1999. *JAMA : the journal of the American Medical Association*. 2001;285(12):1571-1572.

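### Cheap improvement, not an error: the primary t-test on NRS change fixes the baseline slope at 1 and leaves out the site stratum; ANCOVA on baseline NRS and site may narrow the interval with no new data

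*Combined protocol and SAP*

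**What the plan says.** Under Primary Aim, Analyses, the two arms are compared on the "mean difference in NRS from baseline to 3 months using a two-sample t-test", with 95% confidence intervals. Secondary Aim, Analyses, applies the same unadjusted test to SF-12, MODQ, the two timed functional tests and opiate use.

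Two facts in the Procedural protocol bear on this:

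- **Site.** "Patient randomization will be stratified by site and performed through the RedCap database system". No analysis section mentions site again.
- **Baseline.** After the blood draw, "a clinical nurse will administer the PROs and functional assessments and then exit the room". Only then is allocation made: "The research coordinator will perform the randomization through RedCap, and the assigned injectate (PRP or SAI) will be drawn by the physician". Baseline scores therefore precede randomisation.

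The Sample Size section counts on 20 analysable patients per arm. For "potential drop-out or loss to follow-up (estimated at 20%), the investigators will enroll 25 subjects per arm". Amendment 3 withdrew the statistical changes that had accompanied the crossover and the extra pain criterion, so no adjusted model is in force.

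**The concern.** A t-test on change is a baseline-adjusted model whose slope is set to 1 in advance. When the true slope is lower, subtracting the whole baseline adds noise that an estimated slope would remove. Site raises a separate issue. Stratifying balances the arms within site, but a test that ignores site leaves any between-site variation in its error term. If site predicts outcome, the test is then conservative: its type I error falls below 5% and its interval is wider than it need be.

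The trial is small, and at 80% power it can detect only differences of 1.8 to 2.7 NRS points. Amendment 3 returned the enrolment goal to 50, so more patients are not planned. Adjustment is one of the few remaining ways to gain precision.

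**Working it through.** **1. The plan's own figure.** Inputs from Sample Size: 20 per arm, two-sided 5%, SD 2 / 2.5 / 3 with differences 1.8 / 2.3 / 2.7. The noncentrality is difference / (SD × √(2/20)), which gives 2.85, 2.91 and 2.85 on 38 df. Power is 79.2%, 80.9% and 79.2%. Enrolment is 20 / (1 − 0.20) = 25 per arm. Both agree with the plan. The planned 95% half-width is t(0.975, 38) × SD × √(2/20). At SD 2 that is 2.024 × 2 × 0.316 = 1.28 points; at SD 2.5 and 3 it is 1.60 and 1.92.

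**2. Baseline slope.** Let k = SD(baseline)/SD(3 months) and r = their correlation. The true slope is r/k. The residual variance of ANCOVA relative to the change score is

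(1 − r²) / (1 + k² − 2kr),

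which equals 1 only when r = k (slope 1) and reduces to (1 + r)/2 when k = 1. Its square root is the large-sample ratio of CI widths. Example, k = 0.75 and r = 0.3: 0.91 / 1.1125 = 0.818, square root 0.904.

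That ratio ignores the cost of two extra covariates, so the layout was simulated:

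- bivariate normal scores, SD of change 2, difference 1.8;
- 50 randomised at two sites split 17:33, in blocks of 4 within site, with 10 lost at random and 40 analysed;
- ANCOVA on 36 df against the t-test on 38 df; 40,000 runs per scenario; Monte Carlo error about 0.2 points of power.

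The split follows from Sample Size: 43 VA individuals against 9 + about 80 = 89 at the university, or 33%:67%. The block size and random loss are assumptions, as are all values of k and r. The t-test had 78.7–79.3% power and a mean CI width of 2.55 points.

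| k | r | slope r/k | large-sample CI ratio | simulated ANCOVA power |
|---|---|---|---|---|
| 0.75 | 0.3 | 0.40 | 0.904 | 85.2% |
| 0.75 | 0.5 | 0.67 | 0.961 | 80.6% |
| 0.75 | 0.6 | 0.80 | 0.983 | 78.9% |
| 0.6 | 0.3 | 0.50 | 0.954 | 81.2% |
| 0.6 | 0.5 | 0.83 | 0.993 | 77.7% |
| 0.6 | 0.6 | 1.00 | 1.000 | 77.1% |
| 1 | 0.3 | 0.30 | 0.806 | 92.0% |
| 1 | 0.5 | 0.50 | 0.866 | 88.0% |
| 1 | 0.7 | 0.70 | 0.922 | 83.9% |

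In the first six rows the simulated CI runs from 7.8% narrower to 1.9% wider. With equal SDs it is about 18%, 12% and 6% narrower.

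**3. The entry rule.** Requiring baseline NRS of 4 or more shrinks the baseline SD, which might push the slope towards 1. This was simulated directly. Scores were integers from 0 to 10 with unselected mean 5–7, SD 2–3 and r 0.3–0.7 (27 combinations). The underlying SD was the same at both times, the control mean at 3 months was 1.5 points below the unselected mean, and the true difference was 0.9 SD of change (1.8/2). There was no site effect; 20,000 runs each. The rule lowers k to 0.71–0.90 but also lowers r to 0.21–0.64, so the slope stays at 0.29–0.76. ANCOVA power is 78.9–89.4% against 78.1–79.3%, with a CI 0.6–14% narrower. The entry rule alone produced no loss. A loss needs a slope near 1, from extra spread at 3 months.

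**4. Site.** If site explains a share q of the variance of change (4), the gap between sites is √(4q / (0.34 × 0.66)). That is 0.94 points at q = 5% and 1.34 points at q = 10%.

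| q | t-test type I error | ANCOVA power against t-test, slope 1 | same, k = 0.75, r = 0.5 |
|---|---|---|---|
| 5% | 4.4–4.6% | 79.6% against 79.4% | 82.5% against 79.2% |
| 10% | 4.0–4.2% | 81.2% against 79.3% | 84.5% against 79.4% |

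ANCOVA's type I error is 4.7–5.1% throughout.

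**The case against.** The case against is that nothing is broken. The aim, the sample size and the analysis all refer to the same comparison of mean change, and the t-test is valid. That is correct, and it is why this is a recommendation and not a correction.

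Four narrower points carry weight:

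- **The gain is not known.** The correlation, the SD ratio and the site effect are absent from the documents, and the scenarios run from 77.1% to 92.0%. This stands; only the ranges can be defended. The 17:33 split is also rough, because it adds individuals to a count of injections ("performs approximately 80 SIJ injections per year at the University of Utah").
- **The planning SD is ambiguous.** Sample Size does not say whether 2 to 3 is the SD of scores or of change. If 2 is the score SD at both times, the SD of change is 2√(2(1 − r)) = 2.37, 2.00 or 1.55 at r = 0.3, 0.5 or 0.7. The t-test then has 65%, 79% or 95% power for 1.8 points. This moves the absolute figures. It does not change the large-sample ratio of CI widths, which depends only on r and k.
- **Responders may spread the 3-month scores.** Adding an assumed 40–50% of patients with a 60% reduction, under the entry rule, left the CI about 1–8% narrower, against 1–11% without them. The gain shrinks but does not become a loss.
- **Timing.** The analysis plan has already been changed and reverted. The coordinator and the physician know allocations, and Amendment 3 reports a participant discontinued as a treatment failure. A declaration that outcomes by arm were not seen may be hard to make. This is the strongest objection, and it limits when the change can be made.

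No size was calculated for the secondary outcomes.

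**Conclusion.** The point holds as an efficiency gain worth taking, not as a defect. The planned test is valid and reproduces its stated power. With baseline and site already recorded, the trade is lopsided. The worst case tried (slope 1, no site effect) costs 78.7 − 77.1 = 1.6 points of power and a CI 1.9% wider. The best (equal SDs, r = 0.3) gains about 92 − 79 = 13 points and a CI about 18% narrower. Under the NRS entry rule the CI was 0.6–14% narrower in every combination tried. If site explains 5–10% of the variance, ANCOVA gains slightly even at slope 1.

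All these sizes rest on assumed values of r, k and the site effect. Confidence that there is no material downside is good; confidence in any particular gain is moderate at best.

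**What to change.** By dated amendment, before any comparison of outcomes by arm, define the primary analysis as an ANCOVA of 3-month NRS on treatment, baseline NRS and site. Report the adjusted mean difference with its 95% CI. Keep the planned t-test on change as a sensitivity analysis. Use the same model, with each outcome's own baseline plus site, for MODQ, SF-12 and the two timed tests. State in the amendment that it was written without sight of outcomes by arm. If that cannot be stated truthfully, leave the t-test as primary and report the ANCOVA as a sensitivity analysis only.

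The estimand does not change, and no patients or data are added. The cost is two degrees of freedom (36 instead of 38 with 40 analysed), and about 1–2 points of power with a CI up to about 2% wider if the slope is near 1 and site has no effect. It is also one more revision to a plan already revised and reverted, in a trial where some staff know the allocation.

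### The 80%-relief subanalysis estimates PRP versus SAI in that subset but cannot show whether the diagnostic cutoff changes the treatment effect; an exploratory treatment-by-relief interaction would

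*Combined protocol and SAP*

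**What the plan says.** The inclusion criteria under Experimental Design require "50% or greater reduction in pain by a diagnostic anesthetic block". Under Primary Aim, Analyses, the main comparison is "a mean difference in NRS from baseline to 3 months using a two-sample t-test", and the plan adds "The investigators will provide 95% confidence intervals to indicate the uncertainty in these estimates". The same paragraph ends with "A subanalysis will also be performed in subjects who had 80% relief by diagnostic block to determine the effect of the diagnostic cutoff".

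Nothing else in the document analyses block relief. Randomisation is stratified by site only. Amendment 3 withdraws the statistical changes that went with the crossover and the severe-pain entry criterion, and adds nothing here. The document gives no expected size for the 80% subset and does not say whether 80% means at least 80%; I read it that way.

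**The concern.** A cutoff changes the treatment effect only if the PRP-SAI difference is not the same above and below it. That is a difference between two treatment effects, and the plan produces one of them. The only other estimate available to set beside it is the full-cohort result, which includes the subset patients, and no CI is planned for the gap between the two.

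A reader is then left with two informal comparisons, neither of which the plan prescribes. Comparing point estimates or p-values allows chance, or simply the smaller sample, to pass for a cutoff effect. Asking whether the subset CI excludes the overall estimate rarely gives a false signal, but it also seldom picks up a real difference. What is at stake is how a secondary message of the trial report is read, namely whether a stricter block criterion selects patients who respond differently.

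**Working it through.** **Inputs.** From Sample Size: 20 analysed per arm, SD 2 to 3, two-sided 5%, 80% power. From Procedural protocol: equal allocation. My assumption, because the document gives no figure: 30%, 50% or 70% of patients have at least 80% relief, equally in both arms, so m = 6, 10 or 14 per arm.

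**The plan's own figure.** Noncentral-t power at 20 per arm is 79.2%, 80.9% and 79.2% for differences of 1.8, 2.3 and 2.7 at SD 2, 2.5 and 3. The difference giving exactly 80.0% is 0.909 SD. The planned figures are reproduced, and 0.909 SD is used below as the planned effect.

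**The algebra.** Let Ds, Dc and Do be the PRP-SAI differences in the subset, in the remaining patients and overall, and let p = m/20.

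- Do = p·Ds + (1 − p)·Dc, so Ds − Do = (1 − p)·(Ds − Dc).
- SE(Ds − Do) = SD·√(2/m − 2/20).
- SE of the interaction, Ds − Dc, is SD·√(2/m + 2/(20 − m)), tested on 36 df.

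Subset minus overall is therefore the wanted contrast shrunk by the share below 80%. A true 2-point contrast appears on average as 1.4, 1.0 or 0.6 points.

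**Worked line for m = 10.** SE(Ds − Do) = SD·√(0.2 − 0.1) = 0.316 SD, which is 0.632 at SD 2 and 0.949 at SD 3. The chance of a gap of at least 1 point with no true contrast is 11% and 29%. The interaction SE is SD·√(0.2 + 0.2) = 0.632 SD, twice the overall SE of 0.316 SD. Its 95% CI half-width is 2.6 points at SD 2 and 3.9 at SD 3 (unrounded 2.57 and 3.85).

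**All three splits.** The rows on overall significance and on the subset CI excluding the overall estimate come from simulation with 200,000 trials per split; the others are analytic.

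| | 30% (m = 6) | 50% (m = 10) | 70% (m = 14) |
|---|---|---|---|
| *Same effect, 0.909 SD, in everyone* | | | |
| Power of the subset test | 29.7% | 48.6% | 63.9% |
| Subset CI half-width, NRS points | 2.6–3.9 | 1.9–2.8 | 1.6–2.3 |
| Overall significant, subset not | 52% | 33% | 18% |
| Subset and overall differ by ≥1 point | 30–49% | 11–29% | 2–11% |
| Subset CI excludes overall estimate | 2.3% | 0.8% | 0.1% |
| *True contrast of 0.909 SD (1.8–2.7 points)* | | | |
| Share of it seen in subset minus overall | 70% | 50% | 30% |
| Subset CI excludes overall estimate | 13.5% | 9.0% | 1.6% |
| Interaction test significant | 25.0% | 28.8% | 25.0% |
| Interaction CI half-width, NRS points | 2.8–4.2 | 2.6–3.9 | 2.8–4.2 |

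Ranges run from SD 2 to SD 3. For comparison, the overall CI half-width is 1.3 to 1.9 points. Part of the interaction's higher detection rate comes from running at its nominal 5% error rate, whereas the subset-CI rule runs at 0.1% to 2.3%.

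**The case against.** The best reply is that the sentence asks a simpler question. The cutoff is an entry rule, so its effect could mean what the trial would have shown with an 80% rule in place of 50%. On that reading subset against overall is the target, the overlap belongs to it, and nothing is diluted. The identity above also shows that, with equal shares, the estimate below 80% follows from the two planned ones. A correctly scaled test of subset against overall is the interaction test itself: at m = 6, 0.483/0.7 = 0.690, the same SE in SD units. The harm further depends on readers comparing significance labels, which the plan does not propose, and the interaction has little power.

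Much of this stands. The subset result is a sound description of a stricter entry rule, the misreadings are possible rather than planned, and low power is a real limit. It does not rescue the stated purpose. Even on the entry-rule reading, the plan has no contrast with its own standard error or CI, so nothing in it separates a cutoff effect from chance. That the contrast could be reconstructed from the data is a reason to specify it, since it costs almost nothing.

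**Conclusion.** The concern holds, as an optional improvement to an additional analysis. The subset comparison is valid, because the block precedes randomisation, but it cannot by itself determine whether the PRP-SAI difference depends on block relief. If significance is compared informally, between 18% and 52% of trials with one common effect would show an overall result that is lost in the subset.

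These sizes rest on the assumed 30% to 70% share with at least 80% relief, on equal shares in both arms, and on the plan's own SDs and 20 analysed per arm. The structural point does not depend on the share. The primary analysis and the sample size are untouched. The interaction compares patients above and below 80% relief among those enrolled; it says nothing about whether 50% is a suitable entry threshold. One participant entered under the withdrawn severe-pain criterion (Amendment 3) and may have had less than 50% relief; if so, that participant falls in the lower group.

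**What to change.** Replace the sentence with:

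> As an exploratory analysis in all analysed patients, 3-month NRS change will be modelled on treatment, block-relief group (≥80% vs <80%) and their interaction, to explore whether the PRP-SAI difference varies with block relief. The PRP-SAI difference with 95% CI will be reported in both relief groups, with the interaction estimate and its 95% CI. Any statement on the cutoff will rest on the interaction only.

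This keeps the planned ≥80% estimate as one of the two reported. If subset results at the earlier visits are also wanted, the text should say so, because the present sentence names no time point.

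The cost is one sentence and no new data: percent relief must already be known to judge eligibility and to form the planned subset. There are two downsides. The interaction has only 25% to 29% power even for a contrast as large as the planned treatment effect, so a non-significant result is not evidence that the cutoff is irrelevant. Showing both groups also displays more chance variation: with no true contrast, their estimates differ by at least 1 NRS point in 43% to 63% of trials. The reader must therefore rely on the interaction CI, not on the two estimates side by side.
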